6.1.4 Other Protocol-required Therapies

All other protocol-required therapies including dexamethasone and tocilizumab that are commercially available are not provided by Amgen. The investigator will be responsible for obtaining supplies of these protocol-required therapies.

Dexamethasone:

Premedication with dexamethasone is required prior to each AMG 330 treatment cycle and prior to each dose step for the prevention of CRS. Dexamethasone should be administered as a single IV dose (8 mg) within 1 hour of start of AMG 330 infusion or dose step, respectively. Dexamethasone will not be given as a premedication prior to pembrolizumab administration.

Approved

In the case of re-start of AMG 330 infusion after an infusion interruption of > 24 hours, dexamethasone (8 mg IV) should be administered within 1 hour prior to re-start and within 1 hour prior to the dose step.

For administration of dexamethasone after occurrence of CRS or other immune related adverse events, follow guidance in [Section 6.8](#) and [Table 6-3](#).

Tocilizumab:

For administration of tocilizumab after occurrence of CRS, follow guidance in [Section 6.8](#).

Throughout the study, Investigators may prescribe any concomitant medications or treatments deemed necessary to provide adequate supportive care except for those listed in [Section 6.1.7](#). Supportive care may include premedication with anti-emetics to limit treatment-related nausea and vomiting. Subjects should receive medications for treatment-induced diarrhea as clinically indicated. Anti-inflammatory or narcotic analgesics may be offered as needed. Packed red blood cell and platelet transfusions should be administered as clinically indicated.

Concomitant therapies are to be collected from the day of signing the informed consent, through the end of study. For all concomitant therapies collect therapy name, indication, dose, unit, frequency, route, start date, and stop date.

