For an adverse event requiring dose modification, AMG 330 (and pembrolizumab for subjects receiving combination therapy) should be interrupted to allow recovery from the adverse event. Re-initiation of study drug cannot occur until adverse event decreases to grade ≤ 1 . In case of delayed recovery to grade ≤ 1 from treatment-related adverse events that results in a delay of treatment for > 21 days, the subject will not receive additional protocol-related therapy and will be removed from study unless discussed and agreed upon by the sponsor and investigators that it is in the best interest of the subject to receive additional therapy with AMG 330 and pembrolizumab (eg, if subject demonstrated response to therapy).

Assessment of causality (chronology, confounding factors such as disease, concomitant medications, diagnostic tests and previous experience with the agent) must be determined and documented by the investigator, prior to dose modification.

In case of grade 2 CRS, administration of AMG 330 can be continued on the currently tested dose level for 8 hours, and treatment provided to mitigate CRS symptoms. If symptoms do not improve to grade 1, the dose will be de-escalated by 50% for an additional 24 hours. If CRS grade 2 resolves to grade 1, the dose can be re-escalated back to the level being tested. If symptoms persist, AMG 330 infusion will be interrupted and pembrolizumab infusion will be delayed until symptoms improve to grade 1. If treatment is interrupted for < 24 hours, the interrupted AMG 330 dose can be resumed and re-escalated back to the tested dose level. If treatment is interrupted for > 24 hours, restart or repeat rules apply (see below).

In case of grade 3 CRS, AMG 330 treatment must be interrupted and pembrolizumab treatment postponed. Sponsor has to be consulted prior to a planned re-start. In case

of grade 4 CRS, treatment must be permanently discontinued. See [Section 6.8](#) for specific instructions for the management of CRS.

If the same grade 3 non-hematologic adverse event recurs despite a dose reduction, a second dose reduction versus discontinuation of the subject from further protocol therapy should be discussed and agreed upon the sponsor and investigators.

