If a DLT occurs in a subject with clinical benefit from treatment, a restart at a lower dose can be considered if the toxicity has resolved to grade ≤ 1 and after consultation with the sponsor. If AMG 330 is discontinued, pembrolizumab may be continued as a monotherapy until disease progression for a maximum of 35 cycles (approximately 2 years) after discussion and agreement between the sponsor and the investigator. If pembrolizumab is discontinued, AMG 330 may be continued as a monotherapy.

Dose delay: treatment should be interrupted until the adverse event is resolved to grade ≤ 1 , and can then be resumed at the same dose unless the interruption lasted for more than 24 hours, please see below. (Note: if the event needs > 21 days to resolve, treatment has to be permanently discontinued, see also below).

Infusion Interruption

Significant events requiring a change in treatment will be managed by immediate infusion interruption:

- The subject experiences a DLT as defined in [Section 6.2.1](#)
- The subject experiences a clinically relevant grade 4 adverse event related to investigational product (see above) but does not meet the DLT criteria
- The subject meets criteria for discontinuation of investigational product as described in [Section 6.2.2](#)
- The subject experiences disease related adverse events and AMG 330 interruption is required for medical interventions
- Technical problem with the infusion pump
- The investigational product is incorrectly prepared or administered (eg, overdose)

Restarting the Infusion

Treatment may resume if the interruption is ≤ 21 days and if:

- The interruption occurred due to other reasons than toxicity (disease-related events, technical or logistic reasons; eg, diagnostic measurements). The infusion can be restarted at the same dose and without additional measures.
- The toxicity has resolved to CTCAE v5 grade ≤ 1 (in case of dose reduction, infusion may be re-started without prior resolution of the toxicity to CTCAE v5 grade ≤ 1 if the adverse event is not clinically relevant and upon discussion and agreement between the investigator and the sponsor)

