Please also refer to specific guidance on restart after CRS in [Section 6.8](#). Restarting the infusion after a treatment interruption requires care. The re-start should be performed in the hospital, under supervision of the investigator or designee, if the reason for the interruption was other than a technical issue or the interruption exceeded 4 hours independent of reason. Assessments should be performed after infusion re-start depending on the length of the interruption. The subject should be hospitalized for at least 48 hours after re-start of the infusion.

In case of an AMG 330 infusion interruption of > 24 hours, regardless of the reason for interruption, re-start of the infusion (repeat cycle) should be performed using step doses, which will be defined upon consultation with the sponsor. Only 2 repeat cycles may be performed in cycle 1. For cycle 2 and beyond, additional repeat cycles can be permitted upon discussion and agreement between the investigator and sponsor.

Step doses will be performed within 1 – 2 weeks (\pm 1 day) to return to the interrupted AMG 330 dose level, and the number and duration of repeat step doses will depend on the level of interrupted AMG 330 dose. During this 1-2 weeks, [Table 1-7 Schedule of Activities](#) should be followed (eg, for AMG 330 doses interrupted at [REDACTED] μ g/day and below, 2 step doses can be used: [REDACTED] μ g/day for 3 days followed by [REDACTED] μ g/day for 4 days; for doses interrupted above [REDACTED] μ g/day, 3 step doses can be used: [REDACTED] μ g/day for 1 day followed by [REDACTED] μ g/day for 3 days followed by [REDACTED] μ g/day for 3 days). In case of AMG 330 infusion interruption for < 24 hours, regardless of the reason for interruption, restart of infusion should be performed at the same dose level as the last dose level. Administration of pembrolizumab will remain on the Q3W schedule.

After 2 unsuccessful restarts, the subject may remain on the study and continue AMG 330 treatment with a previously tested target dose that has been well tolerated. The dose of pembrolizumab will remain unchanged.

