Dexamethasone (8 mg IV) should be administered within 1 hour prior to re-start and within 1 hour prior to each AMG 330 dose step(s). Dexamethasone is not required prior to the pembrolizumab administration unless it co-occurs with the AMG 330 step dose. In cases when administration of pembrolizumab co-occurs with AMG 330 step, pembrolizumab is administered first followed by dexamethasone followed by AMG 330. The subject should be hospitalized starting from re-start of infusion until 72 hours after the dose step. After each dose level increase, vital signs will be obtained as per the Schedule of Activities (see [Table 1-1](#), [Table 1-3](#), [Table 1-5](#)).

The number of days of exposure to both investigational products before and after an interruption should sum up to at least 70% of planned cumulative dose of AMG 330. In this case, the subject would still be DLT-evaluable. However, if the cycle was interrupted for more than 24 hours but less than 21 days, a new repeat cycle should be started and the interrupted cycle would not be evaluable for DLT, unless the event that lead to the interruption was a DLT.

Note: The end of infusion bone marrow assessment should be performed once it is confirmed that the cycle will not be resumed to assess treatment response. [REDACTED]

[REDACTED]

[REDACTED].

Permanent Discontinuation

A subject will permanently discontinue treatment with investigational product in the event of:

- Dose-limiting or other unmanageable toxicity. Exception: If a DLT occurs in a subject with a clear clinical benefit from treatment a restart at a lower dose can be considered if the toxicity has resolved and after consultation with the sponsor. This includes:
 - Grade 4 CRS
 - Grade 3 CRS occurring at the initial step dose for a cycle (ie, at the 10 µg/day)
 - Grade 2 or 3 CRS meeting any of the criteria listed below:
 - Grade 2 or 3 CRS that does not improve to ≤ grade 1 within 7 days
 - Grade 3 CRS that does not improve to ≤ grade 2 within 5 days
- Re-occurrence of the same grade 4 adverse event
- 3 infusion interruptions > 24 hours in cycle 1
- Disease progression as defined by 2017 European LeukemiaNet (ELN) criteria ([Döhner et al, 2017](#))
- Withdrawal of subject's consent to treatment
- Subject or investigator not compliant with the study protocol
- Occurrence or progression of a medical condition which in the opinion of the investigator should preclude further participation of the subject in the study

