Re-start of Treatment after Infusion Interruption due to Cytokine Release Syndrome:

After interruption of AMG 330 infusion due to grade 3 CRS, the infusion may be re-started if all of the following criteria are met:

- Sponsor must be consulted prior to re-starting treatment
- The event has resolved to grade ≤ 1 prior to re-starting treatment

In case of an infusion interruption of > 24 hours, regardless of the reason for interruption, re-start of the infusion should be performed at the initial dose and dose steps should be performed prior to administering the interrupted dose. The dose level for each step and number of steps should be determined in consultation with the Sponsor prior to re-initiation of the infusion.

Tumor Lysis Syndrome

Subjects with AML and WBC < 10 000/ μ L are considered to be at low risk for tumor lysis syndrome. WBC > 10 000/ μ L and < 50 000/ μ L are considered to be at intermediate risk, and subjects with WBC > 50 000/ μ L are considered at high risk. This protocol requires that subjects have a maximum WBC count of 15 000/ μ L.

Additional high risk features include baseline uric acid > 450 μ g/L (7.5 mg/dL), serum creatinine > 1.4 mg/dL, and lactate dehydrogenase (LDH) greater than the upper limit of normal (ULN).

Patients with intermediate risk WBC count and elevated baseline uric acid (> 450 μ g/L), serum creatinine > 1.4 mg/dL, or LDH greater than ULN will be recommended to receive allopurinol prophylaxis. Typical dosing is 600-800 mg/day administered bid or qid and should begin 3 days before the first dose of study drug. Patients should be well hydrated and supplemented with IV fluid as clinically indicated.

For grade 3 and 4 tumor lysis syndrome, please see [Section 6.2.1](#) for DLT considerations.

Infection Prophylaxis

Subjects who may experience neutropenia for 7 days or longer are at a high risk for infectious complications. As appropriate, these subjects should be administered prophylactic antibacterial (eg, fluoroquinolones), antifungal and antiviral medications. These subjects should be monitored for early signs of breakthrough infections after the initiation of antibacterial therapy to prompt additional evaluation and possible therapy modification.

7. Discontinuation Criteria

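### One restart bullet lets AMG 330 resume at the same dose after a non-toxicity interruption of up to 21 days, contradicting the step-dose, dexamethasone and hospital-restart rules that follow it

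*Protocol*

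**What the plan says.** Protocol Section 6.2.2.1, Restarting the Infusion, allows treatment to resume when the interruption lasted 21 days or less and one of two conditions is met. The first is that the cause was something other than toxicity; disease-related, technical and logistic causes are named. For these it states: "The infusion can be restarted at the same dose and without additional measures".

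The paragraphs that follow set rules by duration and cause:

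- **Dose.** After more than 24 hours, "regardless of the reason for interruption, re-start of the infusion (repeat cycle) should be performed using step doses". A later paragraph adds: "if the cycle was interrupted for more than 24 hours but less than 21 days, a new repeat cycle should be started". Section 6.8, under its CRS restart heading but again covering any cause, says that after more than 24 hours "re-start of the infusion should be performed at the initial dose and dose steps should be performed prior to administering the interrupted dose". Below 24 hours, Section 6.2.2.1 keeps the last dose level.
- **Place.** A supervised hospital restart is required "if the reason for the interruption was other than a technical issue or the interruption exceeded 4 hours independent of reason", with at least 48 hours in hospital afterwards. Sections 6.1.1.2 and 6.1.1.3 repeat the 4-hour threshold (6.1.1.3 allows clinic or hospital).
- **Premedication.** Section 6.1.4 states that "after an infusion interruption of > 24 hours, dexamethasone (8 mg IV) should be administered within 1 hour prior to re-start", and Section 6.7.2 has the same requirement.

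Two sentences on toxicity in Section 6.2.2.1 carry the 24-hour limit. The dose-delay paragraph says treatment "can then be resumed at the same dose unless the interruption lasted for more than 24 hours", and the grade 2 CRS paragraph says: "If treatment is interrupted for > 24 hours, restart or repeat rules apply".

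**The concern.** Taken literally, the bullet permits a restart at the interrupted dose with no steps, no dexamethasone and no hospital supervision after a pause of up to three weeks, provided the cause was not toxicity.

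The measures it drops are the ones the protocol relies on to limit CRS. Section 2.2.2 says dose steps were brought in after grade 3 CRS appeared in the first-in-human study. Section 2.3 names dexamethasone before each step dose as a mitigation for the extra CRS risk that pembrolizumab may bring. CRS was the most frequent adverse event in the first-in-human study: 31 of 49 subjects, 63.3% (Section 4.3).

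There is also a consequence for the primary endpoint. Under Section 6.2.2.1, a cycle interrupted for more than 24 hours but less than 21 days gives way to a repeat cycle, and the interrupted cycle does not count for DLT evaluation unless the event behind the interruption was itself a DLT. A site that follows the bullet may simply carry on with the same cycle. DLT incidence is analysed only in evaluable subjects (SAP Sections 6.2 and 9.6.1), of whom the plan guarantees only 6 per cohort.

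**Working it through.** The plan states no figure on this point, so the check is a comparison of rule text.

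**Inputs.** Scope of the bullet: non-toxicity causes, 21 days or less, no other limit. Dose rule: step doses above 24 h, same dose below 24 h (6.2.2.1; 6.8 for above 24 h). Dexamethasone 8 mg IV: before a restart after more than 24 h (6.1.4, 6.7.2). Hospital restart: any non-technical cause, or more than 4 h for any cause (6.2.2.1; 4-hour rule also in 6.1.1.2 and 6.1.1.3).

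**Cases.** Two kinds of cause (technical; other non-toxicity) by three durations gives 2 × 3 = 6.

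| Cause | Duration | Dose under the other rules | Dexamethasone | Hospital restart | The bullet |
|---|---|---|---|---|---|
| Technical | up to 4 h | same | not triggered | not required | agrees |
| Technical | over 4 to 24 h | same | not triggered | required | omits hospital restart |
| Other | up to 4 h | same | not triggered | required | omits hospital restart |
| Other | over 4 to 24 h | same | not triggered | required | omits hospital restart |
| Technical | over 24 h to 21 days | step doses | required | required | wrong dose; omits both measures |
| Other | over 24 h to 21 days | step doses | required | required | wrong dose; omits both measures |

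Totals: 1 agrees, 3 omit the hospital restart only, 2 conflict on dose, premedication and place; 1 + 3 + 2 = 6.

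**Length of the dose conflict.** The bullet allows up to 21 × 24 = 504 h. The step-dose rule applies to 504 − 24 = 480 h of that, and 480/504 = 95%. This is a share of the permitted range, not of interruptions that will occur.

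**Limits of the count.** Logistic causes are placed under other, because the protocol names them separately from technical ones. Moving them to technical changes which row they fall in, not the 1 + 3 + 2 split. The agreeing case is read generously: the 48-hour stay and the later dexamethasone sentence in 6.2.2.1 do not expressly exclude short technical pauses. Exactly 24 h is not covered by the rules for above and below 24 h; the table puts it with the shorter band only for convenience.

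**Is the bullet a deliberate exemption?** The later rules carry no exception for non-toxicity causes. The only carve-out is in the hospital rule, for technical pauses of up to 4 h. The dose-delay sentence has the 24-hour qualifier that the bullet lacks. Both facts point to a slip.

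**The case against.** The strongest reply is that the conflict is resolved a few lines later. The text directly after the bullet warns that restarting needs care and then sets rules by duration, worded so that the cause does not matter. That stands. A reader might infer that the protocol leaves the choice of rule open, or has no rule for long non-toxicity pauses. The documents support neither reading: there is no formal precedence clause, but the intent is clear.

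A second reply is that the two bullets are only conditions for resuming, so the bullet may mean just that there is no toxicity to wait out and no dose reduction to make. Its example, diagnostic measurements, suggests short pauses. The neighbouring toxicity bullet has no 24-hour limit either, and Section 6.2.2.1 calls its dose-modification and delay criteria general guidelines. This explains how the sentence arose but does not remove the conflict. Naming the restart dose is an explicit dosing instruction, which the neighbouring bullet does not give, and disclaiming further measures contradicts what follows. Guideline status does not reconcile two opposite instructions.

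A third reply is that long non-toxicity pauses may be rare. Section 6.1.1.1 asks that technical and logistic interruptions be kept as short as possible. That also stands, and it limits any claim about frequency.

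**Conclusion.** The concern holds as a local drafting contradiction with a safety consequence. As written, the bullet is wrong on dose and drops two safeguards for every non-toxicity interruption above 24 hours, and it omits the hospital restart in three of the four shorter cases. A site that applies the later paragraphs as well will do the right thing, so the exposure comes from a site acting on the bullet alone.

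The size in patients is unknown. The documents give no frequency of non-toxicity interruptions above 24 hours and no CRS rate after an unstepped restart. A reader might infer from the six-case count that most restarts would be mishandled; it counts rule combinations, not subjects. Nor do the documents show that the DLT result would be biased. The evaluability sentence depends on how long the interruption lasted, so the effect is limited to whether a site starts a repeat cycle or treats the interrupted one as continuing. With as few as 6 evaluable subjects in a cohort, that is enough reason to remove the ambiguity.

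The conclusion rests on reading the later rules as governing, which their wording supports. The edit should be made.

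**What to change.** Replace the second sentence of the first bullet under Restarting the Infusion (Protocol Section 6.2.2.1) with:

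> Resolution to grade ≤ 1 and dose reduction are not required; the restart dose, dexamethasone premedication and hospital-restart requirements follow the rules by duration and reason below (> 4 hours, < 24 hours, > 24 hours).

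This keeps what the bullet can properly say, that there is no toxicity to wait out, and sends everything else to the existing rules. It keeps the hospital restart wherever it applies, including above 24 hours, and makes no new rule for exactly 24 hours. The later paragraphs of 6.2.2.1 and Section 6.8 stay as they are.

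The cost is one sentence in a protocol amendment. The SAP does not restate the restart rule, so it needs no change. No extra subjects or data are needed.

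### In cycle 1, a long AMG 330 interruption followed by two repeat cycles that each end in another one meets both a permission to continue and a mandatory permanent stop

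*Protocol*

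**What the plan says.** All the relevant rules stand in Protocol Section 6.2.2.1.

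Under Restarting the Infusion:
- After any AMG 330 interruption longer than 24 hours, "re-start of the infusion (repeat cycle) should be performed using step doses, which will be defined upon consultation with the sponsor".
- The first cycle carries a cap: "Only 2 repeat cycles may be performed in cycle 1". For later cycles the limit is looser: "For cycle 2 and beyond, additional repeat cycles can be permitted upon discussion and agreement between the investigator and sponsor".
- The permission to go on reads: "After 2 unsuccessful restarts, the subject may remain on the study and continue AMG 330 treatment with a previously tested target dose". It is conditional on good tolerance of that dose. The sentence names no cycle, does not define an unsuccessful restart, and does not refer to the discontinuation list. The pembrolizumab dose stays the same.

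Under Permanent Discontinuation:
- The list is mandatory: "A subject will permanently discontinue treatment with investigational product in the event of" any of the events that follow.
- One of those events is "3 infusion interruptions > 24 hours in cycle 1". No exception is attached to it.
- The list's restart exception belongs to the toxicity item: "If a DLT occurs in a subject with a clear clinical benefit from treatment a restart at a lower dose can be considered". It does not extend to the interruption count.

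Section 6.8 repeats that an interruption over 24 hours calls for a stepped re-start. The SAP summarises re-started cycles (Section 9.6.8) but contains no restart rule, and its DLT definition (Section 5.4) refers back to the protocol.

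**The concern.** A subject can arrive, by one sequence of events, at a sentence that allows further AMG 330 and a sentence that ends treatment. Nothing in the section ranks the two. The section opens by calling its dose-modification and delay criteria general guidelines, so two sites could follow the text in good faith and act differently.

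This matters because the sequence falls in cycle 1, which is the DLT window (Section 6.2.1). What is at stake first is whether the subject is dosed again. The second issue is the primary endpoint. Section 6.2.1 counts a subject as having a DLT if product-related toxicity leaves cumulative AMG 330 below 70% of plan. Stopping or continuing can therefore, in some cases, decide how the subject is classified.

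**Working it through.** The plan gives no figure here to reproduce, so the check is to trace each possible course against both rules.

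**Inputs** (all Section 6.2.2.1): the permission starts after 2 unsuccessful restarts; the stop starts at 3 interruptions over 24 hours in cycle 1; repeat cycles in cycle 1 are limited to 2.

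**Count.** Let N be the number of cycle 1 interruptions over 24 hours. Then N = (1 if the initial interruption exceeds 24 hours) + (1 for each of the two restarts that ends in an interruption over 24 hours).

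An initial interruption can be long (over 24 hours) or short. Each restart can fail in three ways: through a long interruption, through a short one, or without any interruption, for example by not regaining the dose. That gives 2 × 3 × 3 = 18 courses, all within cycle 1.

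| Initial interruption | Long-interruption failures among the two restarts | N | Permission | Mandatory stop |
|---|---|---|---|---|
| Long | 2 | 1 + 2 = 3 | applies | applies |
| Long | 1 | 1 + 1 = 2 | applies | not reached |
| Long | 0 | 1 + 0 = 1 | applies | not reached |
| Short | 2 | 0 + 2 = 2 | applies | not reached |
| Short | 1 | 0 + 1 = 1 | applies | not reached |
| Short | 0 | 0 | applies | not reached |

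The permission column takes the broadest meaning of an unsuccessful restart. Only the first row collides, and it is 1 of the 18 courses. That share is a count of patterns, not a probability.

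**Repeat-cycle limit.** In the colliding course both permitted repeat cycles are used before the third interruption. Resuming after more than 24 hours off drug is by definition another repeat cycle: 2 + 1 = 3, against a limit of 2. In this course the permission cannot be used without exceeding that limit.

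**DLT classification.** Let a be the share of planned cumulative AMG 330 received by the third interruption, and b the further share received if dosing continues. The 70% criterion separates the two rules only if a < 0.70 ≤ a + b. In addition:
- the shortfall must be due to product-related toxicity;
- no DLT may already be on record;
- the criterion's other limb (more than one missed pembrolizumab dose) must not already decide the matter.

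The dose levels are redacted, so a and b cannot be computed.

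**The case against.** The strongest reply is that the section can be read coherently. Repeat step doses exist to bring the subject back to the interrupted dose level. An unsuccessful restart could therefore mean not regaining that level, and the permission would be a fallback dose, not a third re-initiation. The rules then form a sequence: at most two repeat cycles, a tolerated dose if the level is not regained, and a permanent stop at the third long interruption. Reading the permission as covering a third long interruption makes the text conflict with its own limit on repeat cycles. The section also uses restart for interruptions under 24 hours, which never count towards the stop. Finally, a permissive may can be taken to yield to a mandatory will, and re-start steps need sponsor consultation in any case.

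Part of this stands. A reader might infer that every cycle 1 subject whose second restart fails faces opposite rules. The documents do not support that, because in 17 of the 18 courses the stop is not reached. The coherent reading is possible, but the protocol does not state it. A repeat cycle broken off again for more than 24 hours is an unsuccessful restart on any ordinary reading. Sponsor consultation does not tell the sponsor which sentence governs.

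A reader might also infer that each such subject shifts the DLT count by one and so bears on the cohort 2 decision. The documents do not support that either:
- Interruptions count towards the stop whatever their cause, including pump or logistic problems, whereas the 70% criterion needs product-related toxicity.
- Section 6.2.2.1 says a cycle interrupted for more than 24 hours but less than 21 days is not evaluable for DLT unless the cause was a DLT. The subject may then be replaced under Section 4.2.1.
- A subject continuing at a lower dose may fall below 70% anyway.
- The cohort 2 review counts DLTs by day 28 (Section 9.4.1.1). A completed set of repeat steps takes 1 to 2 weeks, and nothing shows that two failed repeat cycles would fall before that day.

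**Conclusion.** The contradiction is real but conditional. It arises in cycle 1 when an initial AMG 330 interruption over 24 hours is followed by two repeat cycles that each end in a further interruption over 24 hours. The finding assumes that such a repeat cycle counts as an unsuccessful restart, which the protocol neither says nor excludes.

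Its main effect is on whether the subject is dosed again within the DLT window. A change in DLT classification is possible but needs all the conditions set out in the check. Any such effect would fall on the full-cycle DLT summary. The number of subjects affected cannot be estimated from the documents. The point should be resolved because the correction is cheap and the text leaves a dosing decision open to opposite answers.

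**What to change.** Reconcile the two parts of Section 6.2.2.1:

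1. Define an unsuccessful restart.
2. State which cycles and which interruption lengths the permission to continue covers, and how it fits with the limit of two repeat cycles in cycle 1.
3. State which rule governs when the permission and the discontinuation list both apply, with a cross-reference in each place.

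The sponsor decides which rule stands. The cost is one or two sentences, with no change to sample size or visits.
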